3.4.7 Concomitant medication

Any medications taken by the patient at any time between the date of the first dose (including the date of the first dose) of study treatment up to the date of last dose of study treatment + 90 days in the study will be considered as concomitant medication. Any medication that started prior to the first dose of the study treatment and ended after the first dose or is ongoing will be considered as both prior and concomitant medication.

Allowed and disallowed concomitant medications will be presented by ATC classification and generic term.

3.4.8 Concurrent Chemoradiation Therapy (cCRT)

cCRT must be completed within 1 to 42 days prior to randomization and the first dose of IP (i.e. durvalumab, tremelimumab, or placebo) in this study.

Where radiotherapy is administered with split dosing, the total dose must be derived (i.e. the absolute values from each split dose are to be added together, regardless of the dose per fraction with which they were delivered, and used in the summary of the radiotherapy data.

Where radiotherapy administration is split by differing frequency (once daily with a total dose of 60 to 66 Gy or twice daily with a total dose of 45 Gy), the total dose must still be derived as above but for all other radiotherapy parameters, the frequency with \geq 95% dose received will be used in the analysis.

3.5 Pharmacokinetic and Immunogenicity Variables

3.5.1 Pharmacokinetic analysis

The actual sampling times will be used in the PK calculations. PK concentration data and summary statistics will be tabulated and listed. Individual and mean blood concentration-time profiles will be generated. Methods for handling samples below the lower limit of quantification (LLOQ) are described in Section 4.2.15.

3.5.2 Immunogenicity analysis

Serum samples for ADA assessments will be conducted utilizing a tiered approach (screen, confirm, titer), and ADA data will be collected at scheduled visits shown in the CSP. ADA result from each sample will be reported as either positive or negative. If the sample is positive, the ADA titer will be reported as well. In addition, the presence of neutralizing antibody (nAb) will be tested for all ADA positive samples using a ligand binding assay. The

nAb results will be reported as positive or negative. A patient is defined as being ADA-positive if a positive ADA result is available at any time, including baseline and all post-baseline measurements; otherwise ADA negative.

For each subject, following responses variables will be evaluated for durvalumab and tremelimumab:

- ADA prevalence, defined as the proportion of study population having drug reactive antibodies at any point in time, baseline or post-baseline
- ADA incidence (treatment-emergent ADA), defined as the sum of both treatment-induced and treatment-boosted ADA.
- ADA positive post-baseline and positive at baseline.
- ADA positive post-baseline and not detected at baseline (treatment-induced ADA).
- ADA not detected post-baseline and positive at baseline.
- Treatment-boosted ADA, defined as a baseline positive ADA titer that was boosted to a 4-fold or higher level (greater than the analytical variance of the assay) following drug administration.
- Persistently positive ADA, defined as having at least 2 post-baseline ADA positive measurements with at least 16 weeks (112 days) between the first and last positive measurement (regardless of Baseline result), or an ADA positive result at the last available assessment (regardless of Baseline result).
- Transiently positive ADA, defined as having at least one post-baseline ADA positive measurement and not fulfilling the conditions for persistently positive (regardless of Baseline result).
- nAb positive at any visit

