Vital signs e	X	X	X	X	X	X	X	8.2.3			
ECG f	X			As clinically is	ndicated			8.2.4			
Concomitant medications	<						>	6.4			
Demography, including baseline characteristics and tobacco use	X										
Eligibility criteria	X							5.1, 5.2			
Brain MRI (preferred) or high-quality brain CT with IV contrast g	X			As clinically in	ndicated		·	5.2			
Laboratory assessments											
Clinical chemistry h	X	Xi	X	X	X	X	X	Table 8			
Hematology h	X	Xi	X	X	X	X	X	Table 9			
TSH (reflex free T3 or free T4)	X	$X^k$	X	X	X	X	X	Table 8			
Urinalysis	X			As clinically i	ndicated			Table 10			
Hepatitis B and C and HIV	X							8.2.1			

	Screening a	C1	C2	C3	C4	C5 to C25	C26/ Final Dosi ng Visit			
Week	-6 to -1	0	q4w ±3 days un	less dosing needs t	to be held for toxi	icity reasons	100	For details.		
Day	-42 to -1	1 b	q28days ±3 days ı	q28days ±3 days unless dosing needs to be held for toxicity reasons 701						
Pregnancy test 	X	X	X	X	X	X	X	8.2.1		
Pharmacokinetics										
Durvalumab PK sample (serum)		$X^{m}$	X n			Cycle 5 only n	X n,o	8.5		
Tremelimumab PK sample (serum) p		X m	X n			Cycle 5 and 7 only n		8.5		
Monitoring						•				
WHO/ECOG performance status	X	X	X	X	X	X	X	8.2.5		
AE/SAE assessment q	<						>	8.3		
IP administration										
Durvalumab or placebo r,s		X	X	X	X	X	X	6.1.1.1, 6.1.1.3		
Tremelimumab or placebo r,s		X	X	X	X			6.1.1.2, 6.1.1.3		
Drug accountability				All visi	ts	•		6.3		
Other assessments and assays										
Durvalumab immunogenicity assessment (ADA sampling to identify ADA responses in patient circulation)		X n				Cycle 5, 13 and 20 only n	X n,o	8.5		
Tremelimumab immunogenicity assessment (ADA sampling to identify ADA responses in patient circulation) p		X n				Cycle 5, 7 and 10 only n		8.5		
Whole blood for genotyping (not applicable for China)		X n						8.8		

	Screening a	C1	C2	С3	C4	C5 to C25	C26/ Final Dosi ng Visit			
Week	-6 to -1	0	q4w ±3 days unless dosing needs to be held for toxicity reasons 10					For details,		
Day	-42 to -1	1 b	q28days ±3 days ι	701	see Section					
Whole blood for gene expression (PaxGene-RNA tubes, not applicable for China)		X n	X n		X n			8.8		

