- For women of childbearing potential only. A urine or serum pregnancy test is acceptable. Women of childbearing potential are required to have a pregnancy test within 7 days prior to the first dose of study drug and then every 4 weeks. Pregnancy test may occur on Day 1, but results must be available and reviewed by the treating physician or Investigator prior to commencing an infusion
- Within 10 minutes of the end of infusion.
- Pre-dose, within 60 minutes prior to start of infusion; before tremelimumab infusion in C1 to C4; before durvalumab infusion in C5 and subsequent cycles. Once 600 patients have been randomized, PK and ADA assessments related to tremelimumab will not be required for any newly randomized patients.
- o PK and ADA samples should be collected on the last scheduled cycle of IP (ie, the last cycle of IP that is within the maximum 24 months from the first dose of IP).
- P Samples should **not** be collected for newly-randomized patients once 600 patients have been randomized.

- q For AEs/SAEs reported during screening, additional information such as medical history and concomitant medications may be needed.
- During the combination portion of treatment, tremelimumab or placebo will be administered first; the durvalumab or placebo infusion will start approximately 1 hour (maximum 2 hours) after the end of the tremelimumab or placebo infusion. If there are no clinically significant infusion reactions with the first cycle, and at the discretion of the Investigator, then for all other cycles, the durvalumab or placebo can be given immediately after the tremelimumab or placebo infusion has finished. Once 600 patients have been randomized, patients newly randomized to durvalumab monotherapy or to placebo will receive 1 infusion only. Patients randomized before 600 patients have been randomized will continue to receive infusions as per schedule.
- s Results for LFTs, electrolytes, and creatinine must be available before commencing an infusion (within 3 days) and reviewed by the treating physician or Investigator prior to dosing.
- Samples for soluble factors (plasma) should be collected on Cycles 5, 7, 9, 11, 13, 15, 17, 19, 22, and 25.

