b WHO/ECOG performance status should also be collected at other site visits that the patient attends, if appropriate site staff are available to collect such information. In addition, WHO/ECOG performance status should be provided when information on subsequent anticancer therapy is provided, where possible.

For patients who discontinue their assigned IP following progression, available readings of CT/MRI from local practice will be collected from patients' medical charts while information on subsequent anticancer treatment and/or PFS2 is collected.

d Details of any treatment for LS-SCLC (including surgery and hospitalizations) after the last dose of IP must be recorded in the eCRF. At minimum, the start date and description of the subsequent anticancer therapy must be collected.

e Patients may be contacted in the week following DCOs to confirm survival status. Details of any treatment for LS-SCLC (including surgery and hospitalizations) after the last dose of IP must be recorded in the eCRF.

Free T3 or free T4 will only be measured if TSH is abnormal or if there is clinical suspicion of an AE related to the endocrine system.

- PK samples for durvalumab and its placebo are to be collected 12 weeks (±7 days) after treatment with durvalumab/placebo ends.
- PK samples for tremelimumab and its placebo are to be collected 12 weeks (±7 days) after treatment with tremelimumab/placebo ends. If tremelimumab/placebo PK samples were taken at Cycle 7 as per Table 1, then the 12-week tremelimumab/placebo PK sample does not need to be collected again. Once 600 patients have been randomized, PK samples related to tremelimumab should **not** be collected for any newly randomized patients.
- Immunogenicity samples for durvalumab and its placebo are to be collected 12 weeks (±7 days) and 24 weeks (±7 days) after treatment with the durvalumab/placebo ends.
- Immunogenicity samples for tremelimumab and its placebo are to be collected 12 weeks (±7 days) and 24 weeks (±7 days) after treatment with tremelimumab/placebo ends. If tremelimumab/placebo ADA samples were taken at Cycle 7 and 10 as per Table 1, then these tremelimumab/placebo ADA samples do not need to be collected again. Once 600 patients have been randomized, ADA samples related to tremelimumab should **not** be collected for any newly randomized patients.
- k ePRO LogPads assigned at randomization will be used.

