# 9.5.4 Immunogenicity data

Immunogenicity results will be listed by patient, and a summary will be provided by the number and percentage of patients who develop detectable ADA to durvalumab and to tremelimumab. ADA titer and nAb data will be listed for samples confirmed positive for the presence of ADA.

The effect of immunogenicity as well as the effect of its neutralizing properties on PK, pharmacodynamics, efficacy, and safety will be evaluated, if the data allow.

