2.1.8 ADA analysis sets

The anti-drug antibody (ADA) analysis set includes all patients in the safety analysis set who have non-missing baseline ADA and at least 1 non-missing post-baseline ADA result of the same IP (durvalumab or tremelimumab).

The durvalumab ADA analysis set will consist of all patients in the safety analysis set who have a non-missing baseline durvalumab ADA result and at least one non-missing post-baseline durvalumab ADA result.

The tremelimumab ADA analysis set will consist of all patients in the safety analysis set who have a non-missing baseline tremelimumab ADA result and at least one non-missing post-baseline tremelimumab ADA result.

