4.2.16 Immunogenicity data

The number and percentage of patients who develop detectable ADA to durvalumab and to tremelimumab within each ADA response category listed in Section 3.5.2 will be summarized by treatment group based on the relevant ADA analysis set. Median and range of maximum titer for each category will be provided. The presence of nAb will be reported for samples confirmed positive for the presence of ADA.

The effect of immunogenicity as well as the effect of its neutralizing properties on PK, pharmacodynamics, efficacy, and safety may be evaluated by descriptive summaries, which will be presented by ADA status (positive/negative) in each treatment group, if the data allow.

All measured and collected immunogenicity results will be listed for each patient and each dosing data by treatment group. ADA titer and nAb data will be listed for samples confirmed positive for the presence of ADA. AEs in ADA positive patients by ADA positive category will be listed.

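### Any durvalumab PFS or OS summary by ADA status should handle when ADA turned positive: ever-positive status makes ADA look protective if ADA accrues over time

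*SAP*

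**What the plan says.** The binary status comes from SAP 3.5.2: "A patient is defined as being ADA-positive if a positive ADA result is available at any time, including baseline and all post-baseline measurements"; every other patient is negative. SAP 4.2.16 then says how immunogenicity may be related to outcome: "efficacy, and safety may be evaluated by descriptive summaries, which will be presented by ADA status (positive/negative) in each treatment group, if the data allow". The same sentence covers PK and pharmacodynamics. Protocol 9.5.4 is firmer but also conditional: "efficacy, and safety will be evaluated, if the data allow". Section 6 of the SAP does not list this softening among its changes from the protocol.

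The durvalumab sampling schedule is in Protocol 1.1. Table 1 has a Cycle 1 sample, then "Cycle 5, 13 and 20 only" in the Cycle 5 to 25 column, and its footnote adds: "PK and ADA samples should be collected on the last scheduled cycle of IP". For the period after stopping, Table 2 says: "Immunogenicity samples for durvalumab and its placebo are to be collected 12 weeks (±7 days) and 24 weeks (±7 days) after treatment" ends. Protocol 6.1.2 continues treatment to progression, intolerable toxicity or 24 months. The ADA analysis set (SAP 2.1.8) needs a baseline and at least one post-baseline result.

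SAP 3.5.2 also derives treatment-induced, treatment-boosted and treatment-emergent ADA, and SAP 4.2.16 tabulates those categories. The by-status summaries of effect use the binary label instead. Neither document specifies a landmark, a time-dependent covariate or any other handling of the date on which ADA became positive.

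**The concern.** The label is assigned from the whole follow-up but would be compared on outcomes counted from randomization. A first positive at Cycle 13 can be seen only in a patient still being dosed at week 48, hence generally still progression-free at week 48. That guaranteed time is credited to the ADA-positive group. Longer treatment also brings more samples and more chances of one positive. Both push the same way: good outcome produces the label.

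At stake is how a secondary objective, immunogenicity, is read. A descriptive median or hazard ratio that favours ADA-positive patients could appear with no true effect, and its direction is the reassuring one.

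A second, separate matter is that a patient positive only at baseline, before any drug, is labelled ADA-positive although treatment induced nothing.

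**Working it through.** **What can be reproduced.** The documents give no ADA rate, timing or precision, so there is no plan figure for this point. Protocol 4.3.1 mentions only a low level of immunogenicity. The design medians used as inputs do check: 10 / 0.65 = 15.4 months for PFS and 24 / 0.73 = 32.9 months for OS.

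**Sample counts (durvalumab, post-baseline).** Cycle n falls at week 4(n − 1), so Cycles 5, 13, 20 and 26 are at weeks 16, 48, 76 and 100.
- Stop before Cycle 5: 0 on treatment + 2 after stopping = 2.
- Complete 24 months: 4 + 2 = 6.

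**Chance of the label with no link to outcome.** With baseline positivity b and independent positivity p per sample, P(ever positive) = 1 − (1 − b)(1 − p)^k for k samples. With b = p = 2% (assumed), k = 2 gives 1 − 0.98³ = 5.9% and k = 6 gives 1 − 0.98⁷ = 13.2%. In simulation, patients whose last dose was before week 16 averaged 1.9 samples and 5.6% were ever positive. Those last dosed at week 100 averaged 5.93 samples and 12.9% were.

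**Null simulation.** 400,000 patients per scenario, ADA independent of outcome.
- From the documents: exponential PFS with median 15.4 months, 38 months' accrual, 36 months' follow-up after the last patient, the sampling schedule and the ADA-set rule. The roughly 10% discontinuation for adverse events is from Protocol 2.3.2.1; its spread over 24 months is assumed.
- Assumed: ADA rates, 12% of PFS events being deaths, and median post-progression survival of 16 months (simulated OS median 35.2 months against 32.9 planned). One progression time ends treatment and counts as the PFS event.
- Estimate: one-covariate Cox hazard ratio, ever-positive versus never-positive. The landmark columns use the baseline or Cycle 5 result in event-free patients with a Cycle 5 sample, counted from week 16.

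| Assumed ADA pattern | Baseline positive | Ever positive | PFS HR | OS HR | Landmark PFS HR | Landmark OS HR |
|---|---|---|---|---|---|---|
| 0.5% per sample | 0 | 2.0% | 0.72 | 0.71 | 0.99 | 0.96 |
| 0.5% per sample | 2% | 4.0% | 0.86 | 0.86 | 1.01 | 0.99 |
| 2% per sample | 2% | 9.4% | 0.77 | 0.78 | 0.99 | 0.99 |
| 5% per sample | 0 | 18.0% | 0.72 | 0.73 | 1.00 | 1.01 |
| 2% per year on drug | 0 | 2.6% | 0.69 | 0.72 | 1.00 | 0.98 |
| 10% per year on drug | 0 | 12.3% | 0.66 | 0.70 | 1.00 | 1.01 |
| Early only, 3% | 0 | 3.0% | 1.02 | 1.01 | 1.03 | 1.01 |
| Early only, 3% | 2% | 4.9% | 1.00 | 1.00 | 1.00 | 0.99 |

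Across all accruing scenarios the null ratio is 0.66 to 0.86 for PFS and 0.70 to 0.86 for OS. With a 10-month PFS median it is 0.63 to 0.85 and 0.72 to 0.87. Early-only ADA gives 0.99 to 1.02 at the 15.4-month median. The first two rows show that baseline positives move the ratio towards 1.

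**At the planned arm size.** With 262 patients, 2% baseline positives and 21 to 50 ADA-positive patients on average, the PFS ratio falls below 1 in 88 to 98% of null trials. The 95% interval lies wholly below 1 in 17 to 45%, against 2.5% nominal.

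**Remedies.** A separate null simulation of the same kind gave a PFS ratio of 0.67 to 0.86 for ever-positive status, 0.98 to 1.01 with a time-dependent covariate, and 1.00 to 1.04 with a Cycle 5 landmark.

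**Numbers at the landmark.** 16 weeks = 112 / 30.4375 = 3.68 months, and 2^(−3.68/15.4) = 0.847, so about 0.847 × 262 = 222 patients are event-free. At 0.5 to 3.3% positivity that is about 1 to 7 ADA-positive patients, or about 11 at 5%. At any time, with no baseline positives and an ADA set of 0.969 × 262 = 254, the ever-positive shares of 2.0 to 12.3% give about 5 to 31 patients. The 5%-per-sample extreme (18.0%) gives about 46.

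**The case against.** The strongest reply is that the plan barely commits to this analysis. The SAP summaries are optional, descriptive and dependent on the data. No hazard ratio, model or test by ADA status is specified, and ADA lies outside the multiple testing procedure. The bias also needs ADA that accrues, and nothing in the documents says that it will. Part of the remedy exists already, because SAP 4.2.16 tabulates the treatment-induced and boosted categories. All of this stands, and it limits the weight of the point. It does not remove it. The schedule samples for late ADA, so the summary should remain valid if late ADA is found, and a descriptive estimate carries the same bias as a tested one. The ADA-set rule and the samples after stopping were in the simulation; they did not remove the bias.

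A reader might infer more than the documents support:
- That ADA will look protective in this trial. That depends on unknown timing; with early-only ADA there is no bias.
- That including baseline positives causes the bias. It dilutes it.
- That PK summaries are distorted in the same way. No calculation shows this, and concentrations at fixed visits such as Cycles 2 and 5 do not depend mechanically on time on treatment.
- That tremelimumab is equally affected. Its Cycle 7 and 10 samples stand in for the 12- and 24-week post-treatment samples, so the count hardly depends on staying on treatment.
- That the trial would wrongly declare immunogenicity harmless. The plan draws no such inference, and only the null was simulated, so masking of a real loss of efficacy was not measured.

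**Conclusion.** The point holds for durvalumab PFS and OS summaries by ever-positive ADA status, and only there. If ADA accrues over follow-up, the label is partly a consequence of staying progression-free, and the null hazard ratio is about 0.65 to 0.86. If ADA arises only early, it is about 1.0. These figures rest on assumed ADA rates (0.5 to 5% per sample, or 2 to 10% per year of exposure, with 0 to 2% at baseline) and on exponential PFS at the design median. The labelling of baseline-only positives is a separate and smaller matter. No primary or key secondary test is affected. This is a cheap improvement to a secondary summary, not a threat to the trial's conclusions.

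**What to change.** In SAP 4.2.16, state that any durvalumab PFS or OS summary by ADA will use treatment-emergent ADA, already derived in SAP 3.5.2, as a time-dependent covariate. Each patient counts as negative from randomization until the date of the first treatment-emergent positive sample, and as positive afterwards. Support it with a landmark display at Cycle 5 (week 16), with time counted from that day in patients still at risk. Show baseline-positive, non-boosted patients as their own group, and keep the any-time definition for prevalence only.

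No new samples are needed; the cost is SAP wording and a little more programming. Intervals will be wide because ADA-positive patients are likely to be few: about 1 to 7 of 262 at the landmark and about 5 to 30 at any time under most of the assumed rates. The landmark display also omits ADA first seen after Cycle 5, which is why the time-dependent analysis should lead.

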3.6 Biomarker Variables

Programmed cell death ligand 1 (PD-L1) expression level in tumor cells (TC) and in immune cells (IC) as measured by immunohistochemistry (IHC) staining will be collected. A flag will be derived in the reporting database to identify cases that were outside the recommended cut slide stability, i.e. stained date – sectioned date > 90 days.

Tumor Mutational Burden (TMB) in both tumor tissue and blood samples will be measured.

3.7 Health Care Resource Use

To investigate the impact of treatment and disease on health care resource, the following variables will be captured:

- Planned and unplanned hospital attendances beyond trial protocol mandated visits (including physician visits, emergency room visits, day cases and admissions)
- Primary sign or symptom the patient presents with
- Length of hospital stay
- Length of any time spent in an intensive care unit (ICU)

The length of hospital stay will be calculated as the difference between the date of hospital discharge (or death date) and the start date of hospitalization or start of study drug if the start of study drug is after start date of hospitalization (length of hospital stay = end date of hospitalization - start date of hospitalization + 1). Patients with missing discharge dates will be calculated as the difference between the last day with available data and the start date of hospitalization. The length of ICU stay will be calculated using the same method.

4. ANALYSIS METHODS

4.1 General Principles

All summaries will be presented in tabular format by treatment group, unless otherwise specified. Data will be presented in data listings by treatment group and patient number.

A month is operationally defined to be 30.4375 days. Six months is operationally defined to be 183 days.

The below mentioned general principles will be followed throughout the study:

- Descriptive statistics will be used for all variables, as appropriate. Continuous
 variables will be summarized by the number of observations, mean, standard
 deviation, median, upper and lower quartiles minimum, and maximum. For log
 transformed data it is more appropriate to present geometric mean, coefficient of
 variation, median, minimum and maximum. Categorical variables will be summarized
 by frequency counts and percentages for each category.
- Unless otherwise stated, percentages will be calculated out of the population total and for each treatment group.
- For continuous data, the mean and median will be rounded to 1 additional decimal place compared to the original data. The standard deviation will be rounded to 2

additional decimal places compared to the original data. Minimum and maximum will be displayed with the same accuracy as the original data.

- For categorical data, percentages will be rounded to 1 decimal place.
- P-values will be rounded to 4 decimal places (with the exception of those in the MTP). P-values less than 0.00005 (e.g. 0.00002) will not be rounded to 4 decimal places (e.g. 0.0000) but instead be displayed as <0.0001. P-values output as <0.0001 by statistical software will not be rounded and will be displayed in the same way ('<0.0001'). P-value presented for the MTP will be rounded to 5 decimal places.
- SAS® version 9.4 will be used for all analyses.

Efficacy and PRO data will be summarized and analyzed on the FAS, or combination analysis set where stated. Safety and treatment exposure data will be summarized based on the safety analysis set, or combination safety analysis set where stated. Study population and demography data will be summarized based on the FAS, or combination analysis set where stated.

